Study participants will be compensated for their time spent completing the research procedures for this study, which include the time spent in the Informed Consent process, and completing the study assessments (in person or telephone questionnaires). They are not compensated for the lumbar procedures (LRFA or simulated LRFA with targeted steroid injections) or CBT (AcTIVE-CBT or TBSCE) they receive during the 3 months of main study follow-up, since these are usual clinical care processes appropriate for LRFA-eligible individuals with chronic low back pain. Compensation will be made by checks mailed to participants. Payments will happen after the study visits on the day of randomization, the 3-month follow-up, and again at the end of the optional period of more extended follow-up after 3-months, unless participants express that they would wish instead to be paid monthly. Compensation will be by check, which will usually be mailed to participants within 4-8 weeks after completing each component. However, due to possible delays, participants will be told it could be up to 4 months after completing each component that they will receive payment. Compensation is as follows:

- VISIT 1: Information session, informed consent, and pre-assessment (\$ 35)
- VISIT 2: The 'baseline' study assessment, which involves completing questionnaires (\$ 25)
- VISIT 3: A questionnaire completed by telephone (\$ 10)
- VISIT 4: A questionnaire completed by telephone (\$ 10)
- VISIT 5: A questionnaire completed by telephone (\$ 25)
- Additional compensation for completing all 3 sets of telephone assessments (\$ 15)

• An 'interim survey' questionnaire that may be offered in the event that a participant elects a major change to the interventional spine treatment or behavioral treatment regimen prior to the expected earliest point of unblinding at the 3-month follow-up (\$ 10)

Optional study visits

• VISITS 6-14: If participant decides to continue participation in this study after Visit 5, these are study visits that will take place over the telephone (\$ 10 for each monthly telephone questionnaire). We will clarify that optional study visits will not take place after the formal end of the study, so some participants recruited late during the study will have fewer "optional" study visits that they can complete.

In sum, participants may be reimbursed up to \$120 for completing all study assessments processes over 3 months. In addition, participants may be reimbursed up to a maximum of \$30-90 for optional study assessments between months 4 and 12 and an additional \$10 if an 'interim survey' is completed.

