The randomization process involves:

- 1. Treatment assignments will be stored centrally electronically in a secure database at VAPSHCS. Envelopes containing the treatment assignments (hardcopies) will also be pre-generated.
- 2. We will utilize computer-generated permuted-block randomization to achieve roughly balanced groups. We will use random blocks that are not divulged to the research staff involved in recruitment in order to avoid bias in the recruitment process. Randomization will be stratified by MBB block responses (50-79% vs. ≥80%).
- 3. Reminder emails will be sent to the clinical assistant ([name]) and the 2nd interventional spine attending physician the day before the scheduled procedure to remind them that they will need to obtain the randomization allocation on the day of the procedure, prior to the procedure. The 2nd interventional spine attending physician is the second interventional spine attending physician-other than the treating spine provider, who will be in the room during LRFA or simulated LRFA and take part in these procedures. Similar emails will be sent on the morning of the procedure.
- 4. Prior to the lumbar procedure, the clinical assistant and the 2nd interventional spine attending physician will open the envelopes which reveal the procedural and behavioral treatment allocations. A non-blinded research staff member will be present to facilitate this and be aware of the treatment allocations. These assignments contained in the envelopes will direct the 2nd interventional spine attending physician whether to perform a standard LRFA or the simulated LRFA, and whether the participant will receive AcTIVE-CBT or TBSCE. A primary function of the clinical assistant is to make sure that the 2nd interventional spine attending physician knows and performs the allocated treatment on the day of the procedure.

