The 2nd interventional spine attending physician who will conduct most LRFA and simulated LRFA procedures in this study will be [name], a board-certified Physical Medicine and Rehabilitation (PM&R) physician with subspecialty accreditation in Pain Medicine. For study participants whose treating physician is [name], the 2nd interventional spine attending physician will be [name] or [name]. Drs. [name] and [name] are board-certified anesthesiologist physicians with subspecialty accreditation in Pain Medicine. Drs. [name], [name], and [name] teach LRFA procedures to Pain Medicine fellows in the UW Accreditation Council for Graduate Medical Education (ACGME)-accredited Pain Medicine fellowship. As shown in Table 2, [name] will not be blinded to randomization unless (for a given participant) he is the treating interventional spine provider, in which case he WILL be blinded. Conversely, [name] will be blinded to randomization status, unless (for a given participant) he is acting as the 2nd interventional spine attending physician ([name] will often be the 2nd interventional spine attending physician in those instances when [name] is the treating interventional spine provider). Similarly, [name] will be blinded to randomization status, unless (for a given participant) he is acting as the 2nd interventional spine attending physician ([name] will sometimes be the 2nd interventional spine attending physician in those instances when [name] is the treating interventional spine provider).

LRFA Technique:

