aining Gains and Coping with cks 60 min. session by ilitation psychologist	 Reading Assignments: Chapter 9 (Effective Problem Solving) Chapter 10 (The End of The Beginning) Topics: Setting Goals Applying your coping skills to problems Relapse Prevention Coping with Pain During Flare-Ups
	leep 60 min. session by ilitation psychologist aining Gains and Coping with cks 60 min. session by

the changes made are substantive.

Blinding Strategy:

Blinding with respect to the lumbar procedures (LRFA vs. simulated LRFA):

- 1. Participants and treating interventional spine providers will be blinded to the status of LRFA vs. simulated LRFA. The PI [name] and [name] will not be blinded, since they are the overseeing study clinicians. Further details are provided below in Table 2.
- 2. For blinding purposes, both LRFA and simulated LRFA will be performed in an identical fashion with the exception of medial branch lesioning, which will not be done in the simulated LRFA group, as described above. Duration and sounds of both the LRFA and simulated LRFA procedures will be similar. Both LRFA and simulated LRFA will apply all safety precautions normally used in our facility such as not using general anesthesia, and the use of both sensory and motor stimulation to avoid incorrect electrode placement (described further below).

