
Additionally, interested Veterans who are given contact information related to the study by the treating interventional spine provider may contact research staff to initiate eligibility screening or assessments at any time.

Screening:

We define chronic low back pain as low back pain present for at least 3 months.⁸ Low back pain is defined as occurring between the lower posterior margin of the rib cage and the horizontal gluteal fold. Low back pain intensity is measured using the numerical rating scale (NRS), with NRS \geq 4 for study inclusion (i.e., NRS must be 4 or higher). See **Table 4** (placed in Section 5.4 as required by the Protocol format) below for a complete and detailed list of inclusion and exclusion criteria, and rationale/indications for exclusion criteria.

Among other criteria, eligible patients will be identified based on their responses to MBBs performed according to routine clinical practice in the VAPSHCS Pain Clinic. Interventional providers in the VAPSHCS Pain Clinic use either lidocaine or bupivacaine anesthetic. Table 3 lists technical details that must be met for MBBs to be counted as 'positive responses'. These criteria will be assessed by research staff, with clarifications as needed by the PI and the treating interventional spine provider. Table 3 and Table 4 assume that the 1st set of MBBs is performed with lidocaine and the 2nd set of MBBs is performed with bupivacaine as per our usual practice. However, clinicians may, for clinical reasons, elect to perform the 1st set of MBBs with lidocaine and the 2nd sets with lidocaine, or both the 1st and 2nd sets with bupivacaine. Any of these combinations are acceptable for the purposes of this study provided that 2 sets of MBBs are used for screening (Table 3).

	1 st set of MBBs (part of Initial	2 st set of MBBs (part of Final	
	Screening criteria)	Screening criteria)	
Anesthetic Type	Lidocaine	Bupivacaine	
Anesthetic volume	0.5 cc	0.5 cc	
Use of contrast to confirm proper positioning at the medial branch and absence of intra-vascular placement	Yes	Yes	
Time window for onset of relief of typical low back pain symptoms	within 30 mins	within 30 mins	
Expected duration of pain relief	<12 hours	<36 hours	

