- iii. Participants who do wear their Fitbit unit on at least 3 of 7 days during the test period, for 6 hours at least each day during the participant's regular waking hours will be classified as being 'Fitbit-complaint'. Participants who do NOT wear their Fitbit unit on at least 3 of 7 days during the test period, for 6 hours at least each day during the participant's regular waking hours will be classified as 'non-Fitbit compliant'.
- iv. Participants who cannot be contacted at least once during the run-in period will be considered to have failed the run-period. They will be excluded from study participation and will not be randomized.

D. Reassessment of study criteria on the day of randomization (Visit 2):

- i. Initial Screening Criteria will be repeated, as per Table 4 (but not including MBBs). Individuals who no longer meet screening criteria will not be randomized and will not be followed further as part of the study.
- ii. Randomization will take place as described further below.
- iii. The lumbar procedure (LRFA or simulated LRFA) will be performed as per the processes described below.
- iv. Subjects will be given a 2nd study participation pledge form. This version of the pledge form will include the items listed on the 1st pledge form, without information pertinent to the run-in period, but will also include additional details that are specific to each participant's CBT allocation (AcTIVE-CBT vs. TBSCE). Specifically, the AcTIVE-CBT pledge form will encourage the participant to use their Fitbit, and try to gradually increase their daily walking while in the study (Attachment O Pledge Visit 2 Extended). As previously, subjects will have a chance to read the pledge and ask questions, and confirm verbally that they understand the pledge and agree to its content. The participant can keep the pledge form. TBSCE participants will also read a pledge form (Attachment N Pledge Visit 2 Brief), which is the same as (Attachment O Pledge Visit 2 Extended), except it does not specifically encourage active Fitbit engagement, and recommends against using the Fitbit Group or Friend functions.
- v. At the time the 2nd study pledge form is provided by a research staff member, the staff member will will ask the "Post-procedure questions". These involve 1-4 questions, which inquire about the participant's immediate impression of whether they received LRFA, or simulated LRFA.
- E. Approach Letters.

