- i. In certain situations, potential participants for SELECT may not be captured by the pre-screening and screening processes as described above. Therefore, they may be identified at some point after their 1st set of MBBs have been completed, but when they no longer have an upcoming clinical appointment scheduled when it is possible to approach them in person about the study. In some cases, this may occur between their 2nd set of MBBs and the time of their lumbar RFA procedure. For Veterans who meet this criteria and are identified during the screening process, we will follow the steps below.
- ii. If potential Veteran participants are identified as above, the PI will send an encrypted email to the treating interventional spine provider for the potential participant, and/or contact by telephone. The

interventional spine provider will 1) decide whether the Veteran appears to meet criteria for the study, and 2) approves research staff contacting the patient. Either the interventional spine provider will complete the Interventional Provider Checklist, or the PI will complete based on information from the interventional spine provider and/or the medical record.

- iii. If the Veteran is a potential participant and approved by the interventional spine provider, research staff will mail an approach letter.
- iv. If we do not receive an inquiry from a potential participant within 7 days after the letter was sent, research staff will begin attempts to contact the potential participant. We will leave voicemail messages as needed. If the Veteran is reached, research staff will talk to them at that time or arrange another time to do so, over the phone, or in person. That discussion can be scheduled around the time of an upcoming appointment at the Seattle campus, if convenient for Veteran.
- v. At the time arranged to talk, research staff will provide Veteran with basic information as you would at the initial contact (Visit 0). If a Veteran is not interested and wants to stop talking, staff will end the call. If a Veteran is interested, research staff would proceed with the screening checklist as typically done during a Visit 0.
- vi. If Veteran passes the screening checklist, we would mail him/her the same info he/she would normally get at a Visit 0 (a What to Expect form [approach letter version] and a blank consent)

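### The PI is unblinded to procedure yet clarifies eligibility, so can guess the next allocation better than chance (about 56–70% under assumed blocks); the likely bias is small but avoidable

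*Combined protocol and SAP*

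**What the plan says.** **Protection against selection.** Section 5.1, Randomization, item 2: "We will utilize computer-generated permuted-block randomization to achieve roughly balanced groups". The recruitment safeguard is "random blocks that are not divulged to the research staff involved in recruitment". That item stratifies by MBB response (two levels). Section 5.2, Brief Overview of Recruitment, adds Fitbit compliance (two levels), so there are two or four strata depending on which text governs.

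**Who is unblinded.** Section 5.1, Blinding Strategy, item 1, says that the PI and one other clinician "will not be blinded, since they are the overseeing study clinicians"; Table 2 repeats this. The physician who is 2nd attending for most procedures "will not be blinded to randomization unless (for a given participant) he is the treating interventional spine provider". The other spine physicians are blinded except when they stand in as 2nd attending.

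**Who judges eligibility.** Section 5.2, Screening, on the MBB criteria in Table 3: "These criteria will be assessed by research staff, with clarifications as needed by the PI and the treating interventional spine provider". In Section 5.2, E. Approach Letters, item ii, either the spine provider completes the provider checklist "or the PI will complete based on information from the interventional spine provider and/or the medical record". Under Pre-Screening, the treating provider decides after the MBBs whether to introduce the study. Section 5.2, D, repeats the screening criteria other than MBBs on the day of randomisation: "Individuals who no longer meet screening criteria will not be randomized". It names no one to do this. Section 5.2 and Table 4 also allow entry to be restricted later so as to oversample patients with at least 80% relief, again without naming who decides.

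**Existing separation.** Section 5.1 keeps the 2nd attending out of data collection and further care for that participant. It says nothing about eligibility of later patients.

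**The concern.** Hiding block sizes from recruiters recognises that a predictable sequence can bias recruitment. The safeguard does not reach someone who already knows the running allocations. Such a person needs only the imbalance so far within the stratum, not the block size, because a permuted block must eventually restore balance.

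The PI is placed in that position: unblinded to procedure, and consulted on whether an MBB response counts. A judgement on a borderline case could, consciously or not, lean on the treatment expected next. Such selection happens before randomisation, so an intent-to-treat analysis does not remove it, and Section 5.6 accepts that the sample is too small for much adjustment. At stake are the effect sizes meant to plan the definitive trial.

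**Working it through.** The plan gives no block size and no predictability figure, so there is nothing of its own to reproduce.

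**Inputs from the plan.** Permuted blocks of random size and MBB strata (5.1, Randomization); possibly Fitbit strata (5.2); 1:1 on procedure (5.3); 20 completers from up to 30 recruited (5.1).

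**Assumptions.** Block sizes are multiples of 4, since there are four cells. The guesser names the procedure given less often so far in the stratum and tosses a coin when tied (the Blackwell–Hodges convergence strategy).

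**Step 1. Complete blocks, everything known.** For block size b = 2m, the expected share correct is [m + (4^m / C(2m,m) − 1)/2] / b.

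- b = 4: [2 + (16/6 − 1)/2]/4 = 2.833/4 = 70.8%
- b = 8: [4 + (256/70 − 1)/2]/8 = 5.329/8 = 66.6%
- b = 12: [6 + (4096/924 − 1)/2]/12 = 7.716/12 = 64.3%
- 4 or 8 at random: (2.833 + 5.329)/12 = 68.0%

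**Step 2. This trial's size.** With 20 to 30 patients in two or four strata, many blocks stay unfinished. Simulated share correct, with all earlier allocations and the strata known:

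| Blocks | 2 strata | 4 strata |
|---|---|---|
| 4 | 69–70% | 67–68% |
| 4 or 8 | 66% | 63–65% |
| 8 | 64–65% | 60–63% |
| 4, 8 or 12 | 63–64% | 60–63% |
| 12 | 61–62% | 56–60% |

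The span is about 56–70%.

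**Step 3. Less knowledge.**

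- One to three others randomised between judgement and allocation (20 patients): about 56–64% for blocks of 4, and 57–62% for 4 or 8. Larger blocks start lower.
- All allocations known, strata unknown: about 53–64%.
- Part of the sequence known, as for physicians who sometimes act as 2nd attending: 55–62% if three quarters is known, 53–58% if half, 52–54% if one quarter.

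**Step 4. Size of the bias.** Let s be the share of patients whose entry is steered, g the prognostic gap between those admitted under one guess and those admitted under the other, and p the share of correct guesses. Expected bias in the procedure contrast is s × g × (2p − 1). Take s = 25% and g = 1 SD as assumptions:

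- p = 0.56: 0.25 × 1 × 0.12 = 0.03 SD
- p = 0.65: 0.25 × 1 × 0.30 = 0.075 SD
- p = 0.70: 0.25 × 1 × 0.40 = 0.10 SD

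The standard error of the procedure main effect with 10 against 10 is √(1/10 + 1/10) = 0.45 SD. Even at p = 0.70 the bias is 0.10/0.45, or about 22% of one standard error.

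**The case against.** The PI's discretion is narrow. Study staff pre-screen all patients scheduled for MBBs, research staff assess the MBB criteria, and the relief percentage comes from a formula on patient-reported scores. For approach-letter candidates the spine provider decides whether criteria appear to be met; the PI may only fill in the checklist. All of this stands, and it limits the opportunity without removing it.

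Timing also helps the plan. Table 5 puts final screening one to four weeks before randomisation. If Fitbit status is a stratum, it is settled only in the run-in after Visit 1, so the stratum may be unknown when the MBB response is judged. Step 3 allows for both.

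Three stronger readings are tempting, and the documents do not support them.

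- **A hit rate of 64–71% for everyone who is unblinded.** The upper end needs a single unstratified list in complete blocks of 4, whereas the plan stratifies and uses random blocks. Nor does the rate fit the attendings: the usual 2nd attending does not see his own patients' allocations, and the others see only cases where they stood in.
- **The PI steering entry on the day itself.** The Visit 2 re-check leaves out MBBs and is not assigned to the PI.
- **Steering that visibly moves the effect sizes.** Step 4 points the other way, in a pilot that disclaims power.

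Finally, the personnel sections (apparently 1.0 and 4.0) are not in the public text. A separation of roles stated there cannot be ruled out.

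**Conclusion.** The overlap is real. The PI is unblinded to procedure and has a documented part in eligibility, and no available text separates the two roles. Withholding block sizes from recruiters does not close the gap.

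The PI's hit rate is about 56–70%, against 50% under concealment, and about 56–64% with a lag of one to three randomisations in small blocks. These figures rest on assumed blocks of 4 to 12, two to four strata, and a PI who actually learns every procedure allocation. The plan leaves the PI unblinded, but the randomisation steps describe communication with the PI only about the CBT arm, so 56–70% is close to an upper range. For physicians who sometimes act as 2nd attending, about 52–62% is realistic.

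Under the assumptions of Step 4 the bias is small relative to sampling error. The point is an avoidable weakness in allocation concealment, not evidence that the pilot's estimates would be materially distorted.

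**What to change.** 1. **Section 5.2, Screening, and E. Approach Letters, item ii.** Remove the PI from MBB eligibility clarifications and from completing the provider checklist. Leave both to the treating interventional spine provider, already named in each place, and to research staff who know no earlier procedure allocation.
2. **Section 5.2, D, and the Table 3 text on oversampling** (repeated under Initial Screening and in Table 4). State that the Visit 2 re-check, and any decision to restrict entry to patients with at least 80% relief, are made by staff without knowledge of earlier procedure allocations. This would exclude the non-blinded research staff member, whose part in screening the plan does not state.
3. **Where the treating provider has previously acted as 2nd attending.** Have research staff record and lock the criteria-based eligibility result before any input from that provider.
4. **Sections 5.1 and 5.2.** Reconcile the stratification factors, since the number of strata affects predictability.

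The cost is slight scheduling friction and less PI input on borderline cases. Two stricter options are harder to defend. Requiring a spine provider who has never acted as 2nd attending may be unworkable, because Table 2 has the listed spine physicians filling that role at times. Blinding the PI by default would reverse a deliberate choice that Table 2 ties to responsibility for clinical issues.

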5.3 Informed Consent Procedures

VA Puget Sound IRB Protocol Template - Version 1.0: 04/2018
A Waiver of Informed Consent was obtained to cover screening/recruitment procedures. Informed consent for study participation is as described below.

A. Informed Consent:

We will obtain written consent from potential study participants following the final screening, after completion of the 2nd set of MBBs.

During Informed Consent, potential RCT participants will:

- i. Receive basic information concerning the overall study goals, which involve simultaneous randomization to 2 types of active treatment: procedural treatments that target the lumbar facet joints, and behavioral treatments based on principles of CBT for chronic pain.
- ii. Receive detailed information concerning the study procedures;
- iii. Have the opportunity to consider all available options for treatment of pain;
- iv. Receive adequate time to raise questions and voice concerns;
- v. Be questioned to assure that they understand all information provided;
- vi. Provide written voluntary consent to participate in continued screening processes.

B. Detailed Description of Informed Consent:

In the section below, all uses of the word 'patients' prior to completion and signing of the informed consent form (ICF) refers to potential candidates for study participation beyond the Informed Consent. Please see the Informed Consent documents themselves.

Patients will be informed during the consenting process that if they are determined to be fully eligible for the study and choose to participate, they will be randomized to LRFA or a simulated LRFA procedure including targeted steroid injections to the facet nerves, and to two types of telehealth-administered behavioral treatments for pain (one brief, one extended). All treatments (both the procedural treatments and behavioral treatments) are "active" treatments expected to improve pain and/or pain-related functional limitations, and all are standard of care treatments in the US.

Because in routine clinical practice our experience has been that patients receiving invasive lumbar pain procedures such as LRFA and lumbar steroid injections are often unclear of some specifics of these procedures and their risks, our informed consent document differs from typical recommendations in that it enumerates the specific physical risks of these procedures, even though these involve the same risks as performed in routine clinical care. We have chosen this route to ensure that participants are fully informed. However, if the IRB reviewers' have further questions or recommend that these risks of usual care practices are omitted, we will be happy to provide further information and/or revise accordingly.

Study staff will describe that radiofrequency ablation (LRFA) is a widely used therapy for relieving low back pain, but that there remains debate about its effectiveness, whether other less invasive procedures may be equivalent (such as steroid injections) and whether long-term negative sequelae from LRFA can involve the joints, adjacent muscles or intervertebral discs. Patients will be informed that there is some possibility that at least some of the pain-relieving effect of LRFA may not be due to the nerve destruction itself, but due to the local anesthesia used, the direct mechanical effect of the needles/electrodes on the tissues in the back, nonspecific effects, or other things that we do not know yet. Patients will also receive a description of the targeted steroid injections that will be administered as part of the simulated LRFA control procedure, and how these procedures may have therapeutic effects, without possible long-term negative sequelae from nerve destruction (as in LRFA) involved joints, or adjacent muscles or intervertebral discs. Patients will also be informed that there is also

uncertainty about the true effectiveness of targeted steroid injections, similar to the situation with LRFA effectiveness. The risks of the LRFA procedure will be discussed, including that it entails applying heat to a nerve that supplies the facet joint (which destroys the nerve at least temporarily) and applying anesthetic around the nerve to the facet joint. Risks will be noted, including infection, bleeding, nerve damage, pain at the injection site, allergic reaction, and worsening of back pain. The risks of the simulated LRFA control procedure with targeted steroid injections will also be discussed, which generally involve the same possible risks as LRFA, but with a lower expected frequency of such risks since the nerves are not destroyed. Patients will be informed that, if they meet all inclusion criteria and are ultimately randomized, they will have a 50% chance (1:1 randomization) that they will not receive LRFA initially, but will receive simulated LRFA with targeted steroid injections instead. Potential risks of enrolling in the trial and being randomized to the control procedure will be discussed, including the trial and being randomized to the control procedure will be discussed, including the possibility that they may continue to experience back pain. Potential benefits of enrolling in the trial and being randomized to the control procedure will be discussed, including the possibility that the patient may have back pain improvement and avoid the need for LRFA, surgery or other interventions for pain and that closer follow-up than usual will be given.

Study staff will also describe to potential participants that many behavioral treatments for CLBP are available, and some (such as CBT) have evidence of effectiveness. However, we don't know what components of CBT-related treatments create these positive effects. We will explain moreover that CBT, even video-based CBT such as the AcTIVE-CBT intervention, consumes substantial Veteran time which may not result in any effects beyond those of the initial education, the provision of written materials, and the formal structure needed for a patient-directed graded, progressive, education and self-management program. Therefore, this study involves comparing two programs of CBT which are delivered by telehealth methods, intended to make it easier for Veterans to access CBT, without the burdens of travel and transportation to repeated face-to-face appointments. One program is an 'extended CBT' program, which involves a program requiring more appointments and video-based sessions with a psychologist (ACTIVE-CBT). The other program is a 'brief CBT' program, which involves a single telephone-based session with a psychologist, and a structured program for education and for the patient to apply the concepts of CBT independently and at their own pace, using formal written materials, with subsequent check-ins by the psychologist as needed (TBSCE). Patients will be informed that, if they meet all inclusion criteria and are ultimately randomized, they will also have a 50% chance (1:1 randomization) of receiving one of these 2 treatments. The extended CBT treatment (AcTIVE-CBT) will involve eight 1-hour video sessions with a psychologist and the provision of educational materials; and the brief CBT treatment (TBSCE) will involve one 1-hour telephone session with a psychologist and the provision of educational materials, with one follow-up phone call by the psychologists approximately 1-2 months after the 1st session of TBSCE, and focused troubleshooting with any problems that might arise. Both treatments will involve the patient needing to wear a Fitbit activity tracker daily for 3 months. However, the AcTIVE-CBT treatment will involve specific therapyrelated interactions surrounding the Fitbit unit. Participants in the AcTIVE-CBT group will be given a 'pledge' form which indicates their intent to try to upload their information to the Fitbit website regularly and consult their Fitbit regularly during the study, to the extent that they are able (Attachment O -Pledge Visit 2 Extended). Participants in the TBSCE group will be given a 'pledge' form which indicates their intent to try to upload their information to the Fitbit website regularly, but will not include prompts for participants to consult their Fitbit during the study, and will ask them not to spend time reviewing their information on the Fitbit website or using the Group or Friend functions, to the extent that they are able, during the first 3 months of the study (Attachment N – Pledge Visit 2 Brief). At the conclusion of the study, unless participants elect not to do so, participants will be provided with an official report containing their study data, including their activity tracker data. Participants may keep the Fitbit unit/s that they use during the study, after study conclusion, irrespective of their group assignment.

In addition, patient consent will include that the study will follow participants for 3 months and collect information on back specific functional status, pain, Fitbit data, health-related quality of life, and other study measures. Potential participants will consent either to data collection for 3 months only, or to also include an ongoing data collection on a monthly basis after the 3-month assessment, for up to 9 additional months, or until the funding period ends (whichever date comes first). Participants may change their mind about the duration of time they wish to participate in data collection at any time during the study.

Potential participants will be informed that, if they choose to participate in the study, they will remain blinded to which study interventional procedure they received (LRFA vs. simulated LRFA) until 3 months. Pledge forms will ask participants to not actively seek out to find answers for which procedural group they are in. At 3 months they will have the opportunity to become unblinded if they wish, and make any usual health care decisions related to CLBP that they wish at that time, with or without the input of their treating physician. This might include having LRFA, irrespective of whether they had already received LRFA or simulated LRFA as part of this study. They will also be informed that if they wish to become unblinded at any time during the study (to seek treatment off protocol for example) or discontinue enrollment in the trial, they can do so. Potential participants will also be told that at 3 months they can be informed about which of the 2 behavioral interventions (AcTIVE-CBT and TBSCE) constituted the official study 'control'. At 3 months they will have the opportunity to become unblinded to this information if they wish, and make any usual health care decisions related to CLBP that they wish at that time, with or without the input of their treating physician. This might include other behavioral treatments including conventional in-person CBT, typical video-based telehealth as offered by the VAPSHCS TREWI program, or others, irrespective of whether they received the AcTIVE-CBT or TBSCE treatment as part of this study. They will also be informed that if they wish to become unblinded at any time (and to pursue usual care outside of the study protocol) or discontinue enrollment in the trial, they will be allowed to do so at their discretion.

The consent process will occur at a time deemed mutually feasible for the Veteran patient and staff member and coordinated on a case-by-case basis. The consent process will take place in a private location (e.g., a medical exam room or private conference room). In most instances, this will take place in the Building 100 Room 7C-130A (in the Pain Clinic clinical area). However, if Room 7C-130A is occupied, this will take place in another unoccupied patient room in the Pain Clinic clinical area, or in Room 7C-14.

A research staff member (see Study Staff Form) will review each section of the IRB-approved ICF, inviting discussion to ensure comprehension. Potential participants will be asked to repeat back understanding of this material as necessary. Individuals will not be permitted to participate if there is any question as to whether a person is able to provide informed consent. Study staff will be trained to ensure competency to discuss informed consent and strategies to ensure there is no coercion. Potential participants will be provided with as much time as needed to review the ICF and ask the research staff member questions about the ICF, their rights as human participants, and participation in the study. Potential participants will be fully informed of all risks and benefits prior to giving their written informed consent and prior to enrollment in the study. To minimize the possibility of coercion or undue influence prospective subjects will be informed that their decision regarding involvement will in no way influence their clinical care and they will be asked if they need some time to consider their involvement before providing consent. All study personnel will have completed the necessary human subjects will be asked if they are able to understand English and whether they feel comfortable speaking it.

If during the course of this contact the potential participant has questions that cannot be addressed by research staff, one of the study investigators or the research manager (depending on the nature of the

questions) will follow up with the potential participant to answer the questions. Potential participants may take time to think about participating and render a decision in a subsequent visit.

Research staff will also review a HIPAA authorization form with the potential participant that permits research staff to review CPRS encounters to extract data collected during treatment. The potential participant will then be asked to sign and date the ICF. Research staff will also date and sign the ICF. All participants will be offered a copy of the signed ICF for their personal records. A note of enrollment will be made in CPRS.

Research staff will file original copies of both the consent and HIPAA forms in the Seattle ERIC offices, kept separate from data collected during screening and subsequent data collected during participation in the study. Research staff will provide participants with staff contact information after the consent process. Participants will also be provided the VAPSHCS research brochure.

